11.7 Analysis of Efficacy Data

The primary efficacy endpoint of percent change in daytime cough frequency (coughs per hour) will be analyzed using a mixed-effects model with sequence, treatment, and time (Day 22) as fixed effects, the baseline value as a covariate, site as a random effect, and subject as a random repeated effect. There will be no imputation for dropouts or missing data for assessments not completed at study visits. A log transformation will be applied to daytime cough frequency; in the presentation of results, log-scale fitted mean treatment group differences at Day 22 will be back-transformed to fitted ratios of geometric means.

As a sensitivity analysis, a negative binomial model will be fitted with the number of coughs at Day 22 as the outcome, with terms for sequence, treatment, and time, as well as baseline cough frequency and subject, and duration of daytime (in hours) as an offset. An autoregressive covariance structure will be assumed for study visits, and the site random effect will use an unstructured covariance matrix.

Secondary efficacy endpoints will be summarized using descriptive statistics. For continuous endpoints (e.g., change from baseline), summaries will include mean, median, standard deviation, minimum, and maximum. For discrete variables (e.g., frequency), summaries will include number of instances and percentage of total instances for that category or time period.

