Daytime cough frequency = ((total cough events for a session not within Sleep, Device Not Attached, Recording Ended Early, Flagged Area event periods) / (recording length in seconds - Sleep, Device Not Attached, Flagged Area event period durations)) x 3600. A session is defined as that 24-hour period when cough recording is taking place for an individual subject. For a session with 'Recording Ended Early', the recording early end datetime will be the end datetime for the session. No events will be collected after the recording early end datetime.

Recording of daytime cough frequency is expected in treatment period 1 at Visit 2 (Study baseline: starting on day -1 and ending at day 1 prior to first IMP intake) and Visit 5 (starting on day 21 and ending on day 22), and in treatment period 2 at Visit 6 (Baseline: starting on day -1 and ending at day 1 prior to first IMP intake) and Visit 9 (starting on day 21 and ending on day 22).

A 24-hour recording is required per protocol at each appropriate visit. All recordings considered valid per Vitalograph[®] quality assessment will be used in analysis, irrespective of actual duration. Cough frequency will be computed based on the actual recording duration.

For the primary endpoint analysis, daytime cough frequency will be log transformed on the natural log scale; ratios will be then calculated per subject per period as log (Visit cough / Study baseline cough) which would represent, upon back transformation and subtraction from 100%, a percent reduction in daytime cough frequency versus study baseline.

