4.11.2 Analysis of Primary Efficacy Variable

The primary variable for the assessment of efficacy is presented at section 3.2.1.1 of this SAP.

The primary analysis for the primary endpoint will be on the natural log scale of the daytime cough frequency data. The difference between NAL ER at 162 mg dose level and placebo will be estimated using a mixed-effects model with sequence, period and treatment as fixed effects, the log-transformed study baseline value as a covariate, , and subject as a random repeated effect.

While measurements taken at different time points are expected to correlate, measurements taken at adjacent time points are assumed to be more correlated than measurements further apart, and therefore the compound symmetry covariance structure will be used.

Sensitivity analysis will be conducted with other covariance structures to evaluate the robustness of the compound symmetry structure considered to model the within-subject errors. The following covariance structures will be utilized respectively:

- 1. Unstructured covariance
- 2. Heterogeneous Toeplitz
- 3. Autoregressive AR(1)

A simplified version will be implemented by excluding the site and gender adjustment. The change from study baseline in log-transformed scale (i.e., log-transformed daytime cough frequency at Day 22 – log-transformed study baseline) will be used as the dependent variable.

In the above defined statistical model, the sequence effect can be interpreted as the carry-over effect: hypothesis testing of sequence effect is equivalent to a test of carry-over effect; should sequence results as non-statistically significant, the sequence effect will be removed from the model, knowing that a carryover effect can be excluded.

There will be no imputation for dropouts or missing data for assessments not completed at study visits. In case of no cough registered in the daytime, in order to allow the log transformation 1 cough will be imputed for derivation of daytime cough frequency.

The following SAS code will be used as reference for the described analysis of primary efficacy endpoint:

```
proc mixed;
class SUBJ SEQ PERIOD TRT;
model log (cough Day 22/ baseline) = PERIOD TRT SEQ / cl alpha=0.05 est
solution;
random site / type=cs sub=SUBJ (SEQ);
estimate 'Day 22: Active - Placebo' trt 1 -1 / e cl;
<Add /modify "Ismeans" and "estimate" statements as needed preserving the
model>
run;
```

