In the presentation of results, log-scale fitted means at Day 22 will be exponentiated back and percentage changes will be presented in table. A code similar to the below will be used:

```
geomean_perc_change=100*(exp(estimate)-1);
sdrerrback=((logStdErr**2)*((100*(exp(Estimate)))**2))**0.5;
geomean_perc_lowercl=geomean_perc_change-(quantile('NORMAL',
0.975)*sdrerrback);
geomean_perc_uppercl=geomean_perc_change+(quantile('NORMAL',
0.975)*sdrerrback);
```

Where SEQ is study Arm (i.e. Arm 1: NAL-ER + Placebo; Arm 2: Placebo + NAL-ER); Period corresponds to the Study Period; TRT is actual treatment received at the time of the assessment (i.e. NAL-ER; Placebo); SITE is the investigational site.

The above described primary analysis will be executed also on the FAS, as well the same analysis will be repeated on completers as a sensitivity analysis.

As an additional sensitivity analysis, a negative binomial model will be fitted with the number of coughs at Day 22 as the outcome, with terms for sequence, and treatment, as well as study baseline cough frequency, and duration of daytime (in hours) as an offset. Site will be a random effect with an unstructured covariance matrix.

Following SAS code will be used as reference for the described sensitivity analysis of primary efficacy endpoint:

```
proc glimmix;
class SEQ TRT PERIOD;
model COUGH = TRT BASE DAYTIME SEQ PERIOD dist=negbinomial solution e cl;
random intercept / subject=SITE type=un;
lsmeans TRT / e cl;
estimate 'Day 22: Active - Placebo' trt 1 -1 / e cl;
<Add /modify "lsmeans", "estimate" statements as needed preserving the model>
run;
```

Where SEQUENCE is study Arm (i.e. Arm 1: NAL-ER + Placebo; Arm 2: Placebo + NAL-ER); TRT is actual treatment received at the time of the assessment (i.e. NAL-ER; Placebo); COUGH is number of coughs at timepoint; BASE is the study baseline cough frequency; DAYTIME is duration of daytime (in hours).

A by subject listing will be provided for primary variable as defined in SAP section 4.2.4.

Daytime cough frequency will be summarized by actual treatment received in terms of absolute values and change from study baseline as defined in SAP section 4.2.5. A similar summary table will be produced for gender and anti-fibrotic therapies subgroups, including presentation of stratified means (SAS PROC SURVEYMEANS may be used).

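### The negative binomial sensitivity model enters baseline cough frequency unlogged under a log link, which inflates its reported standard error, and it leaves the cough count, offset and subject term incompletely specified

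*SAP*

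**What the plan says.** **Sensitivity model.** Protocol 11.7 states that "a negative binomial model will be fitted with the number of coughs at Day 22 as the outcome", with further terms "as well as baseline cough frequency and subject, and duration of daytime (in hours) as an offset". SAP 4.11.2 keeps the count outcome and still describes "duration of daytime (in hours) as an offset", but subject no longer appears in either its prose or its code. The reference code is "model COUGH = TRT BASE DAYTIME SEQ PERIOD dist=negbinomial solution e cl", and the only random effect is "random intercept / subject=SITE type=un". There is no offset option and no link option, so the procedure's default log link applies. The key to the code reads "COUGH is number of coughs at timepoint; BASE is the study baseline cough frequency; DAYTIME is duration of daytime (in hours".

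**Primary model, same section.** The prose names "the log-transformed study baseline value as a covariate". The primary reference code instead uses the log of Day 22 over baseline as the response. Either way, baseline acts on the log scale.

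**Primary variable.** SAP 3.2.1.1 takes as numerator the "total cough events for a session not within Sleep, Device Not Attached, Recording Ended Early, Flagged Area event periods". The denominator is recording time less sleep, unattached and flagged time.

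**Baseline.** SAP 4.2.3 uses the Period 1 (study) baseline in the models, so BASE is the same in both periods for a given subject.

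**Reporting.** SAP 4.11.2 presents this model as a difference in least squares means with CI and p-value, and the primary model as a geometric mean ratio (GMR).

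**The concern.** Under a log link, a raw covariate makes the expected count exponential in baseline. Cough frequency is skewed, and one would expect Day 22 frequency to follow a power of baseline, which is what a log covariate gives. A raw covariate fits badly at the upper end. With no subject term to absorb the misfit, it goes into the dispersion and so into the SE.

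The count is also not tied to awake time in words, and the code does not carry out the offset that the prose describes.

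What is at stake is the usefulness of the check. The covariance variants and the completers repeat all rerun the log-normal model, so this is the only planned inferential check of that distributional assumption. If its CI or p-value differed from the primary result, the reader could not tell a real lack of robustness from a consequence of how the check was specified.

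**Working it through.** **1. The plan's own figure.** The documents give no figure for the negative binomial model, so the planning power was reproduced to fix the scale. Inputs (Protocol 11.1): 44 subjects, CV 1.00, 40% reduction, two-sided 5%. Log SD = sqrt(ln(1 + 1.00²)) = 0.833. SE = 0.833 × sqrt(2/44) = 0.178. |ln 0.6| / SE = 0.511/0.178 = 2.88. Power = Φ(2.88 − 1.96) = 82.1%, or 80.3% with t on 42 df. The stated figure of at least 80% reproduces.

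**2. Shape of the baseline term.** Compare subjects at 200 and 20 coughs/h. If log frequency regresses on log baseline with slope equal to the correlation, the predicted ratio is 10^0.5 = 3.2 at correlation 0.5 and 10^0.85 = 7.1 at 0.85. The fitted raw-baseline slopes in simulation were about 0.011 and 0.02 per cough/h. These predict exp(0.011 × 180) = 7.2 and exp(0.02 × 180) = 36.6.

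**3. Effect on the treatment estimate.** Simulation: 44 completers, true ratio 0.60, log link, log(hours) offset, no subject term, 300 trials per setting. Assumed, not in the documents: median 25 coughs/h, about 16 awake hours (SD 1.2), and the SDs below. Site was not simulated. Correlation = between² / (between² + within²).

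| Between / within log SD | Correlation | Reported SE, raw v log | Ratio | Sampling SD, raw v log | Ratio | Subject-clustered SE, raw v log |
|---|---|---|---|---|---|---|
| 0.7 / 0.3 | 0.84 | 0.099 v 0.083 | 1.19 | 0.070 v 0.069 | 1.01 | 0.069 v 0.068 |
| 0.7 / 0.45 | 0.71 | 0.128 v 0.118 | 1.08 | 0.111 v 0.107 | 1.04 | 0.106 v 0.104 |
| 0.5 / 0.66 | 0.36 | 0.154 v 0.152 | 1.01 | 0.175 v 0.173 | 1.01 | 0.156 v 0.155 |

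The mean estimated ratio was 0.599 to 0.602 throughout. Further runs at correlations 0.5, 0.7 and 0.85 gave a reported SE larger by 3%, 7–9% and 20–22%.

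**4. Role of the subject term.** With no true effect, rejection rates against a nominal 5% were, in the same order of settings:
- raw baseline: 0.7%, 1.3%, 7.7%
- log baseline: 1.7%, 2.7%, 7.3%
- log baseline with subject-clustered SEs, standing in for a subject effect: 5.7%, 5.0%, 8.3%

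The Monte Carlo error is about sqrt(0.05 × 0.95/300) = 1.3 points. Logging the baseline removes only part of the SE misstatement. In the first two settings, respecting the pairing removes the rest.

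**5. Offset against linear covariate.** Entering DAYTIME linearly, as coded, gave SEs of 0.099, 0.129 and 0.155, against 0.099, 0.128 and 0.154 with the log(hours) offset. With hours this uniform the discrepancy costs almost nothing. It could matter more where recordings differ in length, and SAP 3.2.1.1 keeps valid recordings whatever their duration.

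**6. If sleep coughs were counted.** Let s be the placebo share of coughs in sleep and R the treatment ratio in sleep. The count ratio is (1 − s) × 0.60 + s × R. The documents give neither value.
- R = 0.60: exactly 0.60 for any s.
- R = 1.0: 0.608, 0.62, 0.64 and 0.68 for s = 2%, 5%, 10% and 20%.
- R = 0.4: 0.596, 0.59, 0.58 and 0.56 for the same shares.

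**The case against.** **The count is meant to be daytime.** A reader might infer that the model counts all coughs and divides them by awake hours, so that it does not estimate the daytime rate at all. The documents do not support that. The text says neither all nor daytime. The model sits under the primary efficacy variable, which is daytime frequency; its exposure is daytime duration; and the SAP defines 24-hour and sleep frequencies separately. A daytime count is the more natural reading. What remains is an incomplete definition: SAP 3.2.1 describes hourly averages from the vendor, and no daytime count variable is named.

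**The precision argument is weak.** This largely stands. The estimate itself hardly varies more with a raw baseline; mainly its reported SE is wrong. Because study baseline is constant within a subject, its functional form would matter little once a subject effect is present.

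**The correlations are assumed.** This stands too. The planning SE in step 1 is consistent with a total log SD of 0.833 and no correlation, where the raw-baseline penalty was 0.1%. It is equally consistent with a within-subject SD of 0.833, where the penalty was 0% and 5% for between-subject SDs of 0.5 and 0.83. The 20% end needs a within-subject SD of about 0.32.

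**It is only a sensitivity analysis.** True, but its CI and p-value will be presented, and these are what the reported SE governs.

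**Conclusion.** The concern holds as a specification defect in a sensitivity analysis. Baseline enters on the wrong scale for a log link and inconsistently with the primary model. As planned, with no subject term, this inflates the reported SE by roughly 1% to 20% (single runs up to 22%), with the size set by an assumed correlation. Sampling SD rises about 1% to 4%, and the point estimate is practically the same. The sleep-cough question is an ambiguity, with no effect on the ratio unless sleep coughs are counted and the sleep and awake effects differ.

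Two stronger readings should be resisted. One is that the raw baseline materially loses precision: the SE inflation depends on the dropped subject term and all but disappears with subject-clustered SEs (1% to 2%). The other is that the primary result is compromised: nothing here enters the primary model.

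The simulations use 44 completers, assumed SDs and hours, and no site effect. Since SAP 4.15 records that recruitment stopped early, the SE ratios are a better guide than the absolute SEs.

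**What to change.** In SAP 4.11.2, for the negative binomial model:

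- Replace BASE by log(study baseline daytime cough frequency).
- Define COUGH as the number of cough events outside Sleep, Device Not Attached and Flagged Area periods.
- Take the matching awake analysable hours from the 3.2.1.1 formula, and code their log with `offset=` in place of the linear DAYTIME covariate. Unlogged hours should not be used as the offset, because under a log link each extra hour would multiply the expected count by e.
- Restore the subject effect named in Protocol 11.7, in both prose and code. Logging the baseline and defining the count are not enough without this and the offset.
- Report exp(difference in least squares means) with its 95% CI as a rate ratio, beside the GMR.

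The cost is a few words, two variable definitions and three code edits. The count and the awake hours should come from the recordings and event times already collected, so no new data are needed.

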4.11.3.3 EXACT 14-item e-Diary Tool

A by subject listing will be provided for EXACT 14-item e-Diary Tool scores as defined in SAP section 4.2.4.

EXACT 14-item e-Diary Tool scores results will be summarized by actual treatment received and visit in terms of absolute values and changes from study baseline as defined in SAP section 4.2.3;

a ttest will be used to assess statistically significant difference in the changes from study baseline by actual treatment.

A plot showing the absolute mean change from study baseline by actual treatment received will be provided.

This secondary analysis will be executed also on the Completers as a sensitivity analysis.

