11.1 Sample Size and Power

The planned sample size of 44 subjects for the final analysis (22 per sequence) provides at least 80% power to detect a 40% reduction in Day 22 daytime cough frequency (coughs per hour) with NAL ER tablet treatment compared to placebo tablets at the 5% significance level (2-sided). This assumes a CV of 1.00 in log-transformed Day 22 cough frequencies. The CV estimated from *Kelsall et al (2011)* data on chronic cough in patients without esophageal catheterization is 1.12; because Kelsall et al data was on 24-hour cough (including nighttime cough, a period of lower coughing rate) and were not taken in a sample of IPF patients only, it is believed that the CV will be lower than in Kelsall et al data. If the CV is larger than planned at 1.25, this sample size provides > 80% power to detect a 50% reduction from placebo to NAL ER. Alternatively, if the CV is 0.75, this sample size provides > 80% power to detect a 34% reduction from placebo to NAL ER.

A total of approximately 60 subjects will be randomized to ensure complete data from at least 44 subjects, assuming up to potentially a 26% dropout rate.

A statistical update on this Proof-of-Concept (POC) study may be conducted when a minimum of 12 subjects have completed both study periods for the purposes of determining whether POC can be established prior to complete enrollment of the study.

The analysis will be based on conditional power (CP). Futility will be declared if the CP is < 10%, while efficacy will be declared if the CP > 80% (*Mehta and Pocock, 2010*). If the CP is at least 41%, the number of subjects per treatment arm may be changed to recover the targeted power of 80%. If it is evident that the outcome is influenced by a baseline imbalance in disease characteristics then the baseline imbalance will be taken into account in supplemental analyses.

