3.2.1.2.4 E-RS diary

The E-RS daily diary is a derivative instrument of the EXACT consisting of the 11 respiratory symptoms items contained within the 14-item EXACT that measures the effect of treatment on the severity of respiratory symptoms. The E-RS is not administered separately from the EXACT, both a total 14-item EXACT total score will be computed as a secondary efficacy endpoint and a separate analysis of the E-RS 11-items will be done based on the methodology reported in Bacci et al (2018). Bacci et al concluded that analyzing the E-RS daily diary instrument into four separate respiratory symptom domain scales (with no total E-RS score computed) is a valid, reliable and sensitive measure of four distinct respiratory symptoms.

The four domain scales are:

- breathlessness (E-RS items 7, 8, 9, 10, and 11; score range, 0-17)
- cough (E-RS item 2; score range 0-4)
- sputum (E-RS items 3 and 4; score range, 0-8)
- chest symptoms (E-RS items 1, 5, and 6; score range 0-12).

A higher score on the scale indicates a more severe grade to the symptom.

The cough and breathlessness symptom domain scale scores will each be studied as secondary efficacy endpoints.

Questionnaire is recorded daily, the E-RS breathlessness and cough items record collected on the Day 22 visit date will be used as the post baseline value in the summary tables; if a record is not available on the exact date then the last assessment prior to the Day 22 visit date, within a window of 5 days prior to the visit date, will be used. Study baseline value will be the last assessment available prior to the first IMP intake (as defined in this SAP at section 4.2.3).

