4.11.3.4 E-RS diary

E-RS breathlessness (items 7, 8, 9, 10, and 11) and cough items (item 2) will be flagged in the EXACT 14-item e-Diary Tool data listing.

Scores obtained at the E-RS breathlessness scales will be summarized by actual treatment received and visit in terms of absolute values and changes from study baseline as defined in SAP section 4.2.3; a ttest will be used to assess statistically significant difference in the changes from study baseline by actual treatment.

A plot showing the absolute mean change from study baseline by actual treatment received will be provided.

4.11.3.5 This secondary analysis will be executed also on the Completers as a sensitivity analysis. Cough Severity Numerical Rating Scale

A by subject listing will be provided for Cough Severity Numerical Rating Scale as defined in SAP section 4.2.4.

Cough Severity Numerical Rating Scale results will be summarized by actual treatment received and visit in terms of absolute values and changes from study baseline as defined in SAP section 4.2.3.

A plot showing the absolute mean change from study baseline by actual treatment received will be provided.

This secondary analysis will be executed also on the Completers as a sensitivity analysis.

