4.11.3.6 PROMIS Item Bank v1.0 Fatigue Short Form 7a Scale

A by subject listing will be provided for PROMIS Item Bank v1.0 Fatigue Short Form 7a Scale as defined in SAP section 4.2.4.

Cough Severity Numerical Rating Scale results will be summarized by actual treatment received in terms of absolute values and change from study baseline at Day 21 as defined in SAP section 4.2.5.

A plot showing the absolute mean change from study baseline by actual treatment received will be provided.

This secondary analysis will be executed also on the Completers as a sensitivity analysis.

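### EXACT total and E-RS breathlessness are tested with an unspecified t-test that names no pairing, period, sequence or subject term, although the trial is a crossover and the cough-frequency endpoints get a mixed model

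*SAP*

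**What the plan says.** The trial randomises 1:1 to the two orders of NAL ER and placebo (SAP 3.1), so each patient is planned to give a score on both treatments.

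- **EXACT total (SAP 4.11.3.3).** After a summary by treatment and visit, "a ttest will be used to assess statistically significant difference in the changes from study baseline by actual treatment". The analysis is repeated on the completers.
- **E-RS (SAP 4.11.3.4).** "Scores obtained at the E-RS breathlessness scales will be summarized by actual treatment received", followed by the same t-test. In this section the cough item is only flagged in a listing, although SAP 3.2.1.2.4 says that "The cough and breathlessness symptom domain scale scores will each be studied as secondary efficacy endpoints".
- **PROMIS Fatigue (SAP 4.11.3.6).** Under this heading the summary sentence reads "Cough Severity Numerical Rating Scale results will be summarized by actual treatment received", which is a different instrument.
- **Cough frequency (SAP 4.11.2, 4.11.3.1, 4.11.3.2).** The daytime, 24-hour and nighttime rates use a mixed model with sequence, period, treatment, study baseline and subject.
- **General rules.** Efficacy tables pool by treatment received, whatever the period (SAP 4.2.5). One study baseline serves both periods (SAP 4.2.3). The full analysis set (FAS) is primary and the completers are a sensitivity set (SAP 4.5). Secondary endpoints are descriptive by default (SAP 4.11.3), and the protocol plans nothing beyond that for them (Protocol 11.7).

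**The concern.** A t-test between treatment groups treats a patient's two scores as if they came from two people. When those scores are positively correlated, the standard error is too large and a real effect is more easily missed. A paired test avoids this but does not adjust for period, and it can use only patients who have both values. The SAP gives no reason for handling these two scores differently from cough frequency. At stake is whether the trial's tested patient-reported endpoints get the precision that the crossover was chosen to provide.

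**Working it through.** **1. The plan's own power figure.** Protocol 11.1 states: "The planned sample size of 44 subjects for the final analysis (22 per sequence) provides at least 80% power to detect a 40% reduction", two-sided 5%, and "This assumes a CV of 1.00 in log-transformed Day 22 cough frequencies".

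- Log-scale SD = √ln(1 + 1.00²) = 0.8326; effect = ln(0.60) = −0.5108.
- SE = 0.8326 × √(2/44) = 0.1775, so effect/SE = 2.88 in absolute value.
- Noncentral t with 42 df gives 80.3% (43 patients give 79.3%), so the figure reproduces.
- The same inputs in parallel groups of 22 give 51.1%. The stated power therefore depends on comparing treatments within patients.

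This covers daytime cough frequency only. No power is stated for any patient-reported score.

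**2. Which t-test is meant?** Two features favour a two-sample test: the comparison is by actual treatment, in tables that pool over periods; and the analysis runs on the FAS, which admits patients with a single post-baseline assessment, and is then repeated on completers. A paired test on the FAS would use almost the same patients as the completers analysis, so the repeat would add little. Neither feature settles the matter.

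**3. If it is two-sample.** Let ρ be the correlation between a patient's two change scores, and set their SD to 1.

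- True SE of the treatment difference = √(2(1−ρ)/n).
- SE used by the two-sample test = √(2/n).
- Ratio of confidence interval widths, apart from a small difference in df = 1/√(1−ρ).

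The effect d is set so that a paired t-test with n = 44 (43 df) has 80% power. The two-sample test is then applied to the same correlated normal data (80,000 simulated data sets per cell):

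| Assumed ρ | d (SD units) | Two-sample power | Two-sample type I error | CI width ratio |
|---|---|---|---|---|
| 0 | 0.611 | 81% | 5.0% | 1.0 |
| 0.3 | 0.511 | 69% | 2.0% | 1.2 |
| 0.5 | 0.432 | 53% | 0.7% | 1.4 |
| 0.7 | 0.335 | 24% | 0.05% | 1.8 |
| 0.8 | 0.273 | 8% | <0.01% | 2.2 |

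Hand check at ρ = 0.5: 0.432/√(2/44) = 2.026; the critical value on 86 df is 1.988; (2.026 − 1.988)/√0.5 = 0.054, and Φ(0.054) = 52%.

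Recruitment stopped early (SAP 4.15) and the SAP does not give the final number. With an assumed 30 completers the power at ρ = 0.3, 0.5 and 0.7 is 69%, 53% and 25%; with 12 it is 72%, 57% and 30%. The relative loss hardly depends on n.

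**4. A plausible ρ.** The documents give none. Both change scores subtract the same study baseline. Assume that the baseline, Period 1 and Period 2 scores have equal variance (set to 1) and equal pairwise correlation r. Then the covariance of the two changes is r − r − r + 1 = 1 − r, and each variance is 2(1 − r). Their correlation is 0.5 whatever r is. Real data may depart from this, so the range stays in view.

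**5. If it is paired.** Let π be the period effect (Period 2 minus Period 1) and τ the treatment effect. The within-patient difference has mean τ − π in Arm 1 and τ + π in Arm 2. With n₁ and n₂ completers, the paired estimate is biased by π(n₂ − n₁)/(n₁ + n₂). This is zero at the planned 22 per sequence, where period instead adds about π² to the variance of the differences. FAS patients with one period drop out. Under the planning figures, 60 − 44 = 16 randomised patients may lack complete data. How many of them would have one usable period is not known.

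**The case against.** The SAP never says two-sample. Its reference to actual treatment is also its general phrase for presenting tables, so a paired test may have been meant. In that case every figure in the table falls away, and with balanced sequences the missing period term costs only some variance. A two-sample test would also be conservative, so it creates no false claim of benefit. The protocol planned these endpoints as descriptive. All of this stands and limits the size of the point. It does not remove it: the SAP chose to test for significance, and neither reading of the test uses the design fully.

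A reader might go further and infer that E-RS cough and PROMIS Fatigue have no analysis. The documents do not support that. The default in SAP 4.11.3 gives every secondary endpoint a descriptive summary, and SAP 3.2 lists both. SAP 3.2.1.2.4 and 3.2.1.2.6 define the values that enter the summary tables. The instrument name in 4.11.3.6 looks like a copying slip: the sentence sits under the PROMIS heading and refers to Day 21 alone, which is the PROMIS time point, whereas the cough severity scale has three days and its own section. Both endpoints lack a between-treatment test, but so do the cough severity scale and CGI-C, and that agrees with the protocol.

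**Conclusion.** The point holds for EXACT total and E-RS breathlessness: the t-test is under-specified for a crossover, and neither reading is as good as the model already used for cough frequency. The loss of power, from 80% to about 69%, 53% or 24%, depends on the two-sample reading and on assumed correlations of 0.3, 0.5 or 0.7. The middle value follows from equal variances and equal correlations around the shared baseline. There is no such loss at zero correlation or with a paired test, where only the period term and the one-period patients are at issue.

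It would be wrong to infer that a planned power has been missed, because none was stated for these endpoints. For E-RS cough and PROMIS Fatigue the defect is one of wording.

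**What to change.** 1. In SAP 4.11.3.3 and 4.11.3.4, replace the t-test with a linear mixed model on the untransformed change from study baseline: sequence, period and treatment as fixed effects, study baseline score as covariate, and subject as the repeated or random effect. Report the NAL ER minus placebo difference with its 95% confidence interval and p-value. This adjusts for period and keeps one-period patients under a missing-at-random assumption.
2. In 4.11.3.4, name the E-RS cough summary explicitly. The same model could be applied to it, with caution, because it is a single item scored 0 to 4.
3. In 4.11.3.6, replace the cough severity scale by PROMIS Fatigue in the summary sentence.

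The cost is SAP wording and modest programming, with no new data. The reference code in 4.11.2 cannot be copied unchanged: it is written for a log ratio, and its model statement omits the baseline covariate that the text requires.
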